8.8. Quality Control

To maximize data quality the following will be undertaken:

- Provision of standardized instructions on study design, methodology and procedures:
 - Physicians will be contacted via email or telephone and an overview of the study will be provided (detailing study objectives, patient inclusion criteria, correct completion of eCRF and interview and any other logistical aspects of the study);
 - Follow-up with the physicians to ensure queries are resolved quickly.
- The electronic materials will be tested thoroughly to ensure that all questions appear correctly on screen, allow easy interpretation/completion and that all routing and logic checks are working correctly. As such, there should be no missing data (given the online nature of the study, the physician will have to complete a question before he/she is able to move on the next) however, ‘don’t know or unknown’ will be valid responses.
- There will be no monitoring visits or source data verification in this study.

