5.3. Clinical Characteristics

To be abstracted directly from the medical records:

- Date of initial breast cancer diagnosis;
- Stage at initial breast cancer diagnosis;

-
- Date of ABC/mBC diagnosis;
 - Stage of ABC/mBC diagnosis (eg, locoregionally advanced or metastatic);
 - Site of metastases at metastatic diagnosis;
 - Degree of involvement of metastases (eg, single vs. multiple lesions);
 - Patient's performance status at initiation of palbociclib, as scored using the Eastern Cooperative Oncology Group scale or Karnofsky scale;
 - Patient's current performance status, if applicable;
 - Family history of breast cancer;
 - Biomarker status (BRCA, Androgen receptor, ESR1 mutation);
 - Comorbidities diagnosed in the 12 months prior to palbociclib initiation.

To be Derived:

- Time from initial breast cancer diagnosis to ABC/mBC diagnosis.

5.4. Prior Treatment for Early Breast Cancer**To be abstracted directly from the medical records:**

- Category of treatment received (eg, surgery, radiotherapy, neoadjuvant treatment, adjuvant chemotherapy, adjuvant endocrine therapy);
- Adjuvant endocrine therapy start and end dates;
- Reason for stopping adjuvant endocrine therapy (eg, regimen complete, disease recurrence, patient preference, side effects/toxicity, other).

To be Derived:

- Duration of adjuvant endocrine therapy;
- Disease Free Interval, defined as time from regimen completion of adjuvant therapy to diagnosis of ABC/mBC.

5.5. Treatment Patterns for Advanced or Metastatic Breast Cancer**To be abstracted directly from the medical records:**

- Number of lines of therapy received for ABC/mBC at the time of medical record abstraction;

-
- Treatment(s) received in each line of therapy;
 - Start and stop dates of each treatment within each line of therapy;
 - Receipt of palbociclib therapies, by combination partner;
 - Reason for regimen end (eg, disease progression, disease progression following initial control/response, Disease progression without initial control/response, Treatment cost, pill burden/compliance, side effects/toxicity, patient request, other);
 - Date of disease progression for each regimen (if applicable).

To be derived:

- Time from initial breast cancer diagnosis to palbociclib initiation;
- Time from advanced/metastatic diagnosis to palbociclib initiation;
- Duration of each line of therapy;
- Duration of ongoing and discontinued palbociclib treatment;
- Distribution of therapies received post palbociclib discontinuation;

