6. HANDLING OF MISSING VALUES

Subjects with missing values for a particular endpoint will not contribute to the analysis of that endpoint. Missing data will not be imputed.

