7.2.1. Definitions of Clinical Outcomes

Objective Response Rate (ORR)

Objective response rate defined as the proportion of patients achieving complete or partial response on palbociclib combination therapy.

Clinical Benefit Rate (CBR)

Clinical benefit rate is defined as the proportion of patients achieving complete or partial response, or stable disease ≥ 24 weeks on palbociclib combination therapy. Stable disease will be defined as no evidence of complete or partial response, and no progression on palbociclib therapy for 24 weeks or greater.

CCI [Redacted]

[Redacted]

Progression Free Survival (PFS)

Progression Free Survival is defined as the time from palbociclib combination treatment initiation until the earliest of (1) clinician-documented progression while on palbociclib (2) death, (3) start of a new therapy line after final palbociclib dose if the reason for discontinuation of palbociclib was disease progression, or (4) last available follow-up. Patients who did not experience a progression event (items 1, 2 and 3) will be censored at date of last available follow-up. PFS (in months) will be calculated as (first event date - palbociclib initiation date + 1)/30.4.

PFS will be analysed using a Kaplan-Meier (KM) survivor function. A table will show the survivor rate at 3 month intervals and will also show the 3 month incremental survivor rate, ie, the survivor rate from the start of that 3 month interval rather than from time zero. The median survival (if the median is reached) and a KM chart will also be shown. Time zero will be taken at the point of palbociclib initiation.

CCI [Redacted]

[Redacted]

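### PFS item 3 dates a stop for progression only by the start of a next line, so a patient with no usable progression date is counted late, or not at all while alive

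*SAP*

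**What the plan says.** SAP section 7.2.1 measures PFS from palbociclib initiation. Item 1 is "clinician-documented progression while on palbociclib", item 2 is death, and item 3 is the "start of a new therapy line after final palbociclib dose if the reason for discontinuation of palbociclib was disease progression". The remainder are handled thus: "Patients who did not experience a progression event (items 1, 2 and 3) will be censored at date of last available follow-up". The estimator is also stated: "PFS will be analysed using a Kaplan-Meier (KM) survivor function", with survivor rates at 3-month intervals and the median.

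The fields behind the rule are listed in SAP section 5.5 and Appendix 1 Table 3. They are a progression date for each regimen (CRF G2e), the reason for ending the regimen, with several progression codes (G2d), and "Start and stop dates of each treatment within each line of therapy" (G2b/c). The PFS rule does not use the palbociclib stop date.

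Three other places bear on the point:

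- SAP section 5.5 and Appendix 1 Table 6 define PFS as time to first progression or death, with no next-line item.
- SAP section 6 states: "Subjects with missing values for a particular endpoint will not contribute to the analysis of that endpoint". It also rules out imputation.
- Protocol section 8.8 makes every eCRF question compulsory, but answers of the unknown type "will be valid responses". It plans no source data verification.

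**The concern.** Take a patient whose eCRF gives progression as the reason for stopping palbociclib but holds no usable progression date. Progression was known by the day palbociclib stopped. Item 3 ignores that day and waits for another event, the start of a next line. This has two consequences. If a next line starts, the event is late by the whole treatment gap. If none starts, items 1 and 3 never apply: she stays at risk as progression-free until death or last follow-up, against her own record.

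Appendix 1 Table 6 labels PFS exploratory, but progression-free proportions at set times belong to primary objective 6, and SAP section 7.2 takes time-point rates from the Kaplan-Meier life tables. Protocol section 8.1 presents the data as suitable for direct comparison across markets. A dating rule that depends on complete records and on access to a later line could act differently by country. The documents do not allow that difference to be sized.

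**Working it through.** **1. The rule applied to one patient.** Progression at T, stop reason progression, date unknown, gap g to the next line, death at D, last follow-up at C.

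- Next line started by C: event at T + g instead of T.
- No next line, D before C: event at D instead of T.
- No next line, alive at C: censored at C instead of an event at T.

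No affected patient's time is shortened. This step needs no assumption beyond the text.

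**2. Whether another section repairs it.** The shorter definitions in SAP section 5.5 and Appendix 1 Table 6 give no date for this patient. SAP section 6 would drop her. Dropping removes known progressions, so it also raises PFS (step 5). The SAP does not say which rule prevails.

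**3. Inputs for size.** The plan states no figure on this point, so there is none to reproduce. From the documents: medians of 10.8 months (fulvestrant, protocol section 6) and 24.8 months (letrozole, both documents), and minimum follow-up of 3 and 6 months. Assumed: exponential time to progression; follow-up uniform from the minimum to 36 months; 5-30% of progressions undated; 10-40% of those with no next line; a gap of 1 month; mean time from progression to death without a next line of 6, 12 or 24 months (exponential).

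Benchmark: S(t) = 2^(-t/m). For fulvestrant, S(18) = 2^(-18/10.8) = 31.5%.

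**4. Result of the current rule** (simulation, 400,000 patients per row; Monte Carlo error about 0.1 month):

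| Undated | No next line | Mean months to death | Fulvestrant median (true 10.8) | AI median (true 24.8) | Fulvestrant 18-month rate (true 31.5%) |
|---|---|---|---|---|---|
| 5% | 10% | 6 | 10.9 | 24.9 | 31.8% |
| 5% | 10% | 24 | 10.9 | 25.0 | 31.7% |
| 10% | 20% | 6 | 11.0 | 25.1 | 32.0% |
| 10% | 20% | 24 | 11.1 | 25.4 | 32.5% |
| 30% | 40% | 6 | 11.7 | 25.8 | 33.8% |
| 30% | 40% | 12 | 12.2 | 26.6 | 35.6% |
| 30% | 40% | 24 | 12.6 | 27.6 | 37.2% |
| 30% | 40% | no deaths | 13.2 | 30.2 | 40.0% |

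Repeat runs of the 24-month worst case gave an AI median of 27.6 or 27.7. With a 12-month mean to death, about 40% of the no-next-line group end censored and 60% become events at death.

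A separate set of runs varied the mean gap from 0.5 to 2 months, with follow-up to 30 months (fulvestrant) or 36 months (AI) and a 12-month mean to death. The medians rose by 0.1 to 1.6 months (fulvestrant) and 0.1 to 2.0 months (AI). Starting from the 9.2 months that the SAP quotes for fulvestrant, the rise was again 0.1 to 1.6.

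**5. Alternatives on the scenarios of step 4.** Dating the event at the stop date, assumed 0.25 month after progression, keeps both medians within about 0.1 month of the true value. Excluding these patients under SAP section 6 gives 11.0-12.9 months (fulvestrant) and 25.7-33.2 months (AI).

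**The case against.** The strongest reply is that few patients may be affected. Progression date has its own field for each regimen, an answer is forced, and the protocol expects no missing data. At 5% undated and 10% of those without a next line, the medians move by only 0.1 to 0.2 month, which hardly matters in a descriptive convenience sample. This stands as a limit on size. It does not make the rule correct, and the plan would not show which case applies.

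Second, the SAP does not say that item 3 is a fallback for missing dates. It may be meant for progression recorded after the last dose, and a stop reason of progression might itself satisfy item 1. That is possible, but the SAP would then give no date for the event. Section 6 and the shorter definitions also leave open whether such patients are censored or excluded. Both routes overstate PFS.

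Three stronger readings are tempting, and the documents do not support them.

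- A reader might infer that every patient without a next line is censored. Death is item 2, so this holds only for those alive at last follow-up.
- A reader might infer that the error always lengthens PFS. It does so in expectation, but a late Kaplan-Meier value in a small group can fall. One event among 10 at risk gives 9/10 = 0.90. Delay it until six others have been censored and it gives 3/4 = 0.75.
- A reader might infer medians of 13 and 30 months. Those need a model in which patients with no further treatment never die (last row of the table).

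**Conclusion.** The point holds. As written, item 3 dates a known progression late when a next line follows. When none follows, it leaves the patient progression-free until death or last follow-up. No other section of the SAP corrects this.

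The direction is upward in expectation. Under the assumptions in the working, the fulvestrant median rises from 10.8 to about 10.9-12.6 months, the AI median from 24.8 to about 24.9-27.7 months, and the fulvestrant 18-month rate from about 31.5% to 32-37%. The shares undated and without a next line, the gap and the survival after progression are all assumptions. If dates are nearly complete, the effect is negligible. The case for change rests on the rule contradicting collected data and on the low cost of mending it, not on the upper end of the range.

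**What to change.** Replace item 3 in SAP section 7.2.1 with: if the reason for ending palbociclib is any disease-progression code and no progression date is recorded, the palbociclib stop date is the event date, whether or not a new line was started; the next-line start date is used only if the stop date is also missing.

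In the same amendment:

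- State that this rule takes precedence over SAP section 6 for PFS, since using the stop date could otherwise be read as imputation.
- Align the PFS and progression-free definitions in SAP section 5.5 and Appendix 1 Table 6 with section 7.2.1.
- Say that a progression date recorded for the palbociclib regimen counts under item 1 even if it falls after the last dose. Otherwise the new item 3 would leave that patient without a progression event.
- Report the number of events dated by each rule, overall and by country.

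Cost: no new data are needed. The stop date may follow true progression somewhat, so a small upward error remains, and PFS becomes slightly less favourable. Core collection is complete for 652 + 162 + 259 + 251 = 1,324 patients (US, Argentina, Canada, Germany core; protocol Table 2), and the US and Argentina report is already written. Those countries need a re-run on existing fields for the pooled report, with a note where figures differ from those already issued.

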8. LIST OF TABLES AND TABLE SHELLS

A list of tables is presented below. Full table shells can be found in [Appendix 1](#)

Table 1. Characteristics of Participating Physicians

Table 2. Demographic Characteristics of Study Population

Table 3. Clinical Characteristics of Study Population

Table 4. Characteristics of Initial Breast Cancer Diagnosis and Early Stage Disease Treatment

Table 5. Characteristics of Advanced or Metastatic Breast Cancer Diagnosis

Table 6. Time from Initial Breast Cancer and ABC/mBC Diagnosis to Initiation of Palbociclib

Table 7. Number of Lines of Therapy Received for ABC/mBC

Table 8. Patient and Treatment Characteristics for First Line ABC/mBC Therapy

Table 9. Patient and Treatment Characteristics for Second Line ABC/mBC Therapy

Table 10. Patient and Treatment Characteristics for Third Line ABC/mBC Therapy

Table 11. Patient and Treatment Characteristics for Fourth Line ABC/mBC Therapy

Table 12. Patient and Treatment Characteristics for Palbociclib Treatment

Table 13. Treatment Regimens Prescribed Pre- and Post- Palbociclib Treatment

Table 14. Palbociclib Dose Changes

Table 15. Supportive Therapies Received During Palbociclib Treatment

Table 16. Recorded Response to Palbociclib Treatment

Table 17. Clinical Outcomes Associated with Palbociclib Treatment

Appendix 1. Table of Variables

Table 1. Demographics and Clinical Characteristics

Variable	Role	Data source(s)	Operational definition
Demographics			
Age when palbociclib was initiated	Primary objective 1	CRF B1	
Menopause natural or induced	Primary objective 1	CRF B2a	
Menopause induced surgically or LHRH	Primary objective 1	CRF B2b	
Ethnic origin	Primary objective 1	CRF B3	
Family history of breast cancer	Primary objective 1	CRF B4	
Biomarker result	Primary objective 1	CRF B5	Multiple responses – BRCA1, BRCA2, Androgen receptor, ESR1 mutation
Insurance type	Primary objective 1	CRF B8	
Concomitant conditions	Primary objective 1	CRF C1	Multiple responses allowed
Clinical characteristics			
ECOG at palbociclib initiation	Primary objective 1	CRF C2a	
ECOG (at time of data collection)	Primary objective 1	CRF C2a	
Karnofsky at palbociclib initiation	Primary objective 1	CRF C2b	
Karnofsky (at time of data collection)	Primary objective 1	CRF C2b	
Vital status	Primary objective 1	CRF BQ6	
Stage at initial breast cancer diagnosis	Primary objective 1	CRF D2	
Time to advanced breast cancer diagnosis	Primary objective 1	CRF E1a, D1	

Variable	Role	Data source(s)	Operational definition
Stage at advance diagnosis	Primary objective 1	CRF E1b	Only too be derived if CRF D2 is Stage 0, I, II, or IIIa
Sites of metastases at advanced diagnosis	Primary objective 1	CRF E2	Multiple responses allowed
Burden of metastases at advanced diagnosis	Primary objective 1	CRF E2	

Table 2. Early Breast Cancer Treatment History

Variable	Role	Data source(s)	Operational definition
Adjuvant therapies received	Primary objective 2	CRF F1	Multiple responses allowed – class level
Duration of adjuvant endocrine therapy	Primary objective 2	CRF F2	
Reason for stopping adjuvant endocrine therapy	Primary objective 2	CRF F2	
Disease free interval	Primary objective 2	CRF F2 , E1a	Time from regimen completion of adjuvant therapy to diagnosis of ABC/mBC

Table 3. Advanced/metastatic Breast Cancer Treatment

Variable	Role	Data source(s)	Operational definition
Line that palbociclib is introduced	Primary objective 3	CRF G2	This line number will be used for the subsequent variables that are relative to palbociclib initiation, eg, if palbociclib is initiated at line 2 then prior will be at line 1 and post will be at line 3, etc.

Variable	Role	Data source(s)	Operational definition
Time to palbociclib initiation	Primary objective 3	CRF G2b	
Treatments received when palbociclib was initiated (T)		CRF G2a	Multiple responses allowed. Each treatment will be listed separately
Treatment combination at T	Primary objective 3	CRF G2a	Mutually exclusive treatment combinations
Is that line still ongoing?	Primary objective 3	CRF G2c	
If not, what was the reason for ending?	Primary objective 3	CRF G2d	
Treatments received in the line prior to palbociclib initiation (T-1)			Multiple responses allowed. Each treatment will be listed separately
Treatment combination at (T-1)	Primary objective 3	CRF G2a	Mutually exclusive treatment combinations
Reason for ending T-1	Primary objective 3	CRF G2d	
Treatments received in the line post palbociclib initiation (T+1)			Multiple responses allowed. Each treatment will be listed separately
Treatment combination at (T+1)	Primary objective 3	CRF G2a	Mutually exclusive treatment combinations
Is that line still ongoing?	Primary objective 3	CRF G2c	
If not, what was the reason for ending?	Primary objective 3	CRF G2d	
The 2nd set of treatments received in the line post palbociclib initiation (T+2)			Multiple responses allowed. Each treatment will be listed separately

Variable	Role	Data source(s)	Operational definition
The 2nd treatment combination at (T+2)	Primary objective 3	CRF G2a	Mutually exclusive treatment combinations
Is that line still ongoing?	Primary objective 3	CRF G2c	
If not, what was the reason for ending?	Primary objective 3	CRF G2d	
Number of treatment lines received	Primary objective 3	CRF G2a	
Duration of each line of therapy	Primary objective 3	CRF G2b/c	
Duration of ongoing palbociclib treatment	Primary objective 3	CRF G2b/c	
Duration of discontinued palbociclib treatment	Primary objective 3	CRF G2b/c	
Frequency that tumour response is assessed	Primary objective 6	CRF I1a	
Date of disease progression for each regimen (if applicable)	Primary objective 6	CRF G2e	

Table 4. Palbociclib Dosing Details

Variable	Role	Data source(s)	Operational definition
Initial dose	Primary objective 4	CRF H1	
Reasons for starting dose lower than 125 mg/day	Primary objective 4	CRF H1b	
Number of dose changes	Primary objective 4	CRF H2	
Number of dose changes	Primary objective 4	CRF H3	Including zeros, ie, no changes stated in CRF H2
Any dose reductions?	Primary objective 4	CRF H3b	
Any dose increases?	Primary objective 4	CRF H3b	

Variable	Role	Data source(s)	Operational definition
Any dose interruptions?	Primary objective 4	CRF H3b	
Dose resumed	Primary objective 4	CRF H3b	
Number of interruptions	Primary objective 4	CRF H3b	Including zeros, ie, no interruptions
Duration of interruptions	Primary objective 4	CRF H3a	
Any cycle delays?	Primary objective 4	CRF H3b	
Duration of cycle delays	Primary objective 4	CRF H3a	
Reasons for dose change	Primary objective 4	CRF H3c	Multiple responses allowed. Reduce to patient level, ie, if “lack of response” is ticked for any dose changes then “lack of response” is considered ticked
Status of combination partner therapy when dose is changed	Primary objective 4	CRF H3d	
Time from palbociclib initiation to first dose change	Primary objective 4	CRF H3a	

Table 5. Supportive Therapies Whilst Receiving Palbociclib

Variable	Role	Data source(s)	Operational definition
All supportive therapies received whilst receiving palbociclib	Primary objective 5	CRF H4	Multiple responses allowed

Table 6. Clinical Outcomes

Variable	Role	Data source(s)	Operational definition
CCI			
Progression free survival	Exploratory objective	CRF G2e	Defined as the time from the start of palbociclib to the first subsequent progression or death. The treatment grid in section G will be used to determine in which treatment line that this occurs.
Progression free at 6, 12, 18, 24 months of treatment	Primary objective 6	CRF G2e	Proportion of patients who have not displayed progression at defined time points.
Did the patient achieve complete response whilst receiving palbociclib?	Primary objective 6	TBC	
Time to complete response	Primary objective 6	TBC	
Did the patient achieve partial response whilst receiving palbociclib?	Primary objective 6	TBC	
Time to partial response	Primary objective 6	TBC	
Objective Response Rate	Primary objective 6	CRF I1d/I1e	Proportion of patients who achieve CR/PR at CRF I1d/I1e.

Variable	Role	Data source(s)	Operational definition
Time to Death	Primary objective 6	CRF B7	This will be the time from the start of palbociclib to death. This will only include patients for whom death has been recorded.
CCI			
Survival at 12, 18, 24 months	Primary objective 6	AQ2, BQ7	Proportion of patients who have not died at defined time points.
